8.4.2. Multiple Imputation of Missing DOOR at D5V and D11V

Several analyses depend on multiple imputation of DOOR at D5V or D11V for ITT and ATP analysis populations if a significant number of data are missing. First, a table showing the number and percentage of missing data for DOOR on D5V and D11V will be presented in [Table 20](#). In order to use the multiple imputation model to adjust for bias caused by missing data, we assume that data is missing at random (MAR).

Multiple imputations of each of these missing endpoints will be performed independently, and each subject will have their missing endpoints imputed independently of other subject's imputations using a subject-specific imputation model.

As a first step to multiple imputation, an ordered list of variables to include in the subject-specific imputation model is constructed. Ordering is specified so that exact imputation results from final data are prespecified may be replicated in SAS (using seeds described below). The complete ordered list of variables for the imputation models for DOOR at D5V and OCO at D5V is below.

- Indicator of azithromycin as study treatment (binary indicator)
 - Note: azithromycin is the reference group for study treatment
- Indicator of subject enrolled at the site with the second most number of subjects enrolled (binary indicator)
- Indicator of subject enrolled at the site with the third most number of subjects enrolled (binary indicator)
- Indicator of subject enrolled at the site with the fourth most number of subjects enrolled (binary indicator)
- Indicator of subject enrolled at the site with the least number of subjects enrolled (binary indicator)
 - Note: the site with the most number of subjects enrolled is reference for site. Language is written to allow for an arbitrary number of sites. In the event of a number of ties for the number of subjects enrolled, tied sites will be ordered in ascending alphanumeric order in the list of model variables.
- OCO at D5V (imputed OCOs will not be used)
- Observed clinical improvement at D5V
- Study day of D5V (centered at 5)
- Presence of fever on Day 1 as recorded on the Assessment of LRTI Symptoms and Fever (LRT) form
- Presence of fever in the day preceding or at the D5V as recorded on Solicited Events or vital signs form
- Severity of most severe solicited event on Day 1 (0, 1, 2, or 3)
- Severity of most severe solicited event on Day 2 (0, 1, 2, or 3)
- Severity of most severe solicited event on Day 3 (0, 1, 2, or 3)
- Severity of most severe solicited event on Day 4 (0, 1, 2, or 3)
- Severity of most severe solicited event on D5V study day (0, 1, 2, or 3)

- o Note: The D5V window is Day 1 through Day 8. Therefore, all days from Day 1 through the actual study day of D5V will be listed.

For DOOR and OCO at D11V, the complete list of model variables is identical to the above. Additionally, most severe solicited events are listed up to study day 11 rather than D5V study day and presence of fever in the day preceding or at D11V is used instead of D5V.

The actual list of model variables for each subject-specific imputation model will follow the ordering above but omit variables with missing values. The below pseudo-code / SAS code outlines the creation of 20 multiple imputation datasets. Note that the seeds used in the actual analysis must follow the specification given in the pseudo-code and subjects must be processed in the order described in the pseudo-code. OCO will simultaneously be imputed with DOOR at each respective Outcome Assessment Day. The pseudo-code is in terms of D5V endpoints, but the general logic is also applicable to the D11V endpoints (with references to “D5” replaced with references to “D11”).

```
DEFINE i=index variable for subjects having DOOR imputed.
```

```
    Subjects requiring imputation are sorted in ascending order
    by PATID.
```

```
DEFINE N=number of subjects requiring imputation
```

```
DEFINE g&i=analysis dataset containing predictors and DOOR for
```

```
    CC-D5 subjects as well as subject i (only one subject not in
    CC-D5 included). Note that CC-V1 subjects that are missing a value
    for one or more variables in the subject-specific imputation model are
    excluded.
```

```
DEFINE imp_g&i = g&i, with 20 imputed values for the missing DOOR
    added by PROC MI
```

```
DEFINE &&modelVars_&i = list of observed variables in subject i, to
    be used for imputation of DOOR and OCO.
```

```
%do i=1 %to &N;
```

```
PROC MI data=g&i out=imp_g&i seed=1200&i NIMPUTE=20 noprint;
```

```
    var &&modelVars_&i DOOR OCO;
    monotone reg(DOOR_D5V = &&modelVars_&i);
    monotone reg(OCO_D5V = &&modelVars_&i);
```

```
run;
```

```
%end;
```

imp_g&i will be subset to contain only rows for the subjects with imputed DOOR and merged together and with CC-D5 data to create the twenty complete multiply imputed datasets

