6.3.1. Intention-to-Treat Analysis (ITT) Population

The ITT population will include all subjects with PCT ≤ 0.25 ng/mL randomized to receive study product. The analyses on the ITT population will be performed per randomized treatment assignment. Subjects in the ITT population with missing values for clinical improvement or DOOR will be imputed using multiple imputation. Baseline variables and presence of fever at the timepoint of interest will be used in the multiple imputation model. For DOOR, daily maximum severity of solicited events and OCO will be used in the multiple imputation model.

Subjects randomized but not treated will also be analyzed in the ITT population. If fever and solicited events data are collected post-randomization for a subject that was not treated, that data will be used in the ITT analysis to assist in imputing the clinical improvement and DOOR. For subjects treated with study product, data collected post dose 1 will be used in the imputation model.

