6.5.4. Ordinal Clinical Outcome at D5V or D11V

The OCO at D5V is defined as follows:

If the subject died at any point of study participation, then OCO at D5V will be 8.

Else if the subject has missing clinical improvement at D5V then OCO at D5V will be missing.

Else if the subject did not have clinical improvement at D5V and was hospitalized then OCO at D5V will be 7.

Else if the subject did not have clinical improvement at D5V with ED, outpatient clinic, or urgent care visit but was not hospitalized then OCO at D5V will be 6.

Else if the subject did not have clinical improvement at D5V and did not have any medically attended events then OCO at D5V will be 5.

Else if the subject has missing most severe solicited event at D5V as defined in Section 6.5.3 then OCO at D5V will be missing.

Else if the subject had clinical improvement at D5V and a most severe solicited event of grade 3 at D5V then OCO at D5V will be 4.

Else if the subject had clinical improvement at D5V and a most severe solicited event of grade 2 at D5V then OCO at D5V will be 3.

Else if the subject had clinical improvement at D5V and a most severe solicited event of grade 1 at D5V then OCO at D5V will be 2.

Else if the subject had clinical improvement at D5V and did not experience any solicited event through D5V (i.e.; the most severe solicited event at D5V is of grade 0) then OCO at D5V will be 1.

The OCO at D11V is defined in a similar manner by replacing D5V by D11V in the above algorithm.

Note that in some cases OCO can be defined even if some components are missing. For instance, if a subject had record of receipt of study product and did not have clinical improvement at D5V, OCO at D5V would still be defined even if most severe solicited event at D5V was missing since the above algorithm doesn't take solicited events severity into account for OCO levels 5, 6, 7, and 8.

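### The Day 11 DOOR imputation list keeps the Day 5 outcome variables and omits the observed Day 11 ones, so some known Day 11 improvers are imputed as failures

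*SAP*

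**What the plan says.** SAP 8.4.2 gives an ordered variable list for imputing DOOR and OCO at Day 5. Besides treatment, site, fever and daily solicited-event severity, it contains the Day 5 OCO (observed values only), "Observed clinical improvement at D5V" and the Day 5 visit day.

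For the later visit it says: "For DOOR and OCO at D11V, the complete list of model variables is identical to the above". Two changes follow. Daily severities run to study day 11, and "presence of fever in the day preceding or at D11V is used instead of D5V". Clinical improvement, OCO and visit day at Day 11 are not mentioned.

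SAP 6.5.4 decides who has a missing OCO. After death, missing improvement and the three non-improved levels (7, 6, 5) have been dealt with, it continues: "Else if the subject has missing most severe solicited event at D5V as defined in Section 6.5.3 then OCO at D5V will be missing". The same algorithm applies at Day 11. Under 6.5.3, one missing grade between Day 1 and study day 11 is enough, unless a grade 3 event was recorded.

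**The concern.** The Day 5 model conditions on improvement at the visit being imputed. The Day 11 model, as listed, conditions on improvement at the previous visit. Among subjects whose Day 11 status is known, only improvers can lose their OCO through a gap in solicited-event grades. Missingness for them therefore depends on a variable that the model omits, and the missing-at-random assumption stated in 8.4.2 does not hold for that group given the listed variables. The regression is fitted to complete cases that include all the gap-free failures, so it can give a failure's rank to someone recorded as improved. At stake are the imputed results in Tables 46 and 47.

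**Working it through.** **Who is imputed.** DOOR is missing only if OCO or antibiotic days are missing (SAP 6.5.6). From the order of the 6.5.4 algorithm, for subjects alive with known Day 11 status:

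- P(OCO missing | not improved) = 0, because level 5, 6 or 7 is assigned before solicited events are examined.
- P(OCO missing | improved) = P(a grade is missing and no grade 3 was recorded).

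ATP-11 requires defined Day 11 improvement and five consumed doses, and it keeps subjects with missing DOOR (SAP 6.3, 6.3.2). With dosing documented, antibiotic days should be known (6.5.5). Essentially every imputed DOOR in ATP-11 therefore belongs to a known improver. ITT has three groups:

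- known improvers with a gap in grades;
- subjects with a known OCO but missing antibiotic days, whose Day 11 OCO the list ignores;
- subjects whose Day 11 improvement is itself missing, for whom there is no Day 11 outcome to add.

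**Check of the ranking rule.** The plan gives no figure for this imputation. Its four-subject example in 6.5.6 has scores A 1.05, B 1.00, C 2.00 and D 1.05. These rank as 2.5, 1, 4 and 2.5, as the SAP states.

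**Simulation inputs from the SAP.** 674 randomized, so 337 per arm; 57.6% improved at Day 5; 20 imputations; normal linear regression, with one model per imputed subject fitted to complete cases.

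**Assumptions not in the documents.** Day 11 improvement of 57.6% to 90%; latent Day 5 to Day 11 correlation of 0.3, 0.6 or 0.8; one missing diary day, between Days 6 and 11, in 15% of improvers without a grade 3 event; solicited-event rates of 40% and 30% by arm. There were six replicates per setting.

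**Models compared.** The listed model used treatment, site, Day 5 OCO, Day 5 improvement, visit day, Day 1 fever, Day 11 fever and the observed daily severities. The comparison model put Day 11 improvement in place of Day 5 OCO and improvement. An imputed rank counts as a failure if it exceeds (number of Day 11 improvers + 0.5). An imputed OCO counts as a failure at 4.5 or above.

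Results for known improvers are ranges over the three correlations. Shift means imputed minus full-data DOOR probability.

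| Day 11 rate | OCO in failure range, as listed | Rank in failure range, as listed | Rank, with Day 11 improvement | Shift, as listed | Shift, with Day 11 improvement |
|---|---|---|---|---|---|
| 57.6% | 13.8–21.4% | 28.5–39.1% | 1.5–3.0% | -0.002 to -0.004 | 0.000 to +0.003 |
| 65% | 13.2–18.5% | 21.8–30.4% | 1.5–1.7% | -0.006 to -0.008 | +0.001 |
| 70% | 11.0–13.5% | 18.2–22.2% | 1.6–2.7% | -0.005 to -0.010 | +0.001 to +0.002 |
| 80% | 7.5–8.6% | 12.1–12.9% | 2.6–3.0% | -0.006 to -0.011 | +0.001 to +0.003 |
| 90% | 3.1–3.7% | 6.3–7.6% | 2.9–4.0% | -0.002 to -0.005 | +0.004 to +0.007 |

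On the OCO scale, adding Day 11 improvement brings the failure share to 0–0.4%. The mean imputed OCO is about 1.9 to 3.0 as listed and about 1.5 to 1.6 with Day 11 improvement, against a true mean of about 1.4 to 1.5. The Day 5 model, which includes same-visit improvement, places about 0% (OCO) and 1–2% (rank) in the failure range.

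**More frequent or unequal gaps.** A simpler simulation imputed on treatment and clinical improvement only. It assumed Day 11 improvement of 0.88 after Day 5 improvement and 0.60 otherwise, and event rates of 20% on placebo and 35% on azithromycin.

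- Gaps of 20% in each arm, approximate rerun with event severities assumed: 0.7245 becomes 0.708, a fall of 0.0165.
- Gaps of 30% on placebo and 15% on azithromycin: 0.724 becomes 0.688, a fall of 0.036, and 0.729 with Day 11 improvement added.

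The sampling SD of a DOOR probability at this size is about 0.02.

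**The case against.** The strongest reply is that Day 5 text serves as a template throughout the SAP. Section 8.4.2 says of its pseudo-code that "the general logic is also applicable to the D11V endpoints", with D5 references replaced by D11. Section 8.4.1 likewise lists only the Day 5 visit day, yet 8.2.2 puts the Day 11 visit day in the Day 11 improvement model. Protocol 11.4.3 item 3 asks for information from any completed visit, and SAP 6.3.1 says: "For DOOR, daily maximum severity of solicited events and OCO will be used in the multiple imputation model". A programmer might well make the substitution.

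That shows an alternative reading, but it does not settle the text. The replacement sentence concerns code that names no DOOR predictors. If it covered the list, the separate instruction on Day 11 fever would be unnecessary. The protocol sentence is general and leaves details to the SAP, and 6.3.1 gives no time point. The list is ordered so that results can be reproduced exactly from fixed seeds, and two readings defeat that purpose.

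Several limits do stand. Day 11 symptoms and solicited events come from the same form, so a wholly missing Day 11 form would usually remove the improvement status too. Day 11 fever stays in the model and identifies some failures. Section 8.4.2 makes DOOR imputation conditional on a significant amount of missing data. The footnotes to Tables 46 and 47 already require reading the components and sensitivity analyses.

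**Conclusion.** The point holds as a specification error in an exploratory analysis. The misplacement of known improvers follows from 8.4.2 read with 6.5.4. Its size, about 6% to 39% of imputed ranks against about 1.5% to 4%, rests on the assumed Day 11 rate. The effect on the DOOR probability is probably small: about -0.002 to -0.011 with 15% of improvers having a gap, below the sampling SD of about 0.02. It grows if gaps are more frequent or unequal between arms. At a 90% Day 11 rate the comparison model overshoots by 0.004 to 0.007, so the case for the change rests on using known outcomes and does not promise a closer DOOR probability in every setting.

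A reader might infer more than the documents support:

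- **That the Day 11 DOOR result is materially biased.** The fall from 0.724 to 0.688 is an unequal-gap scenario with a stripped-down model. Nothing in the documents suggests twice as many diary gaps on placebo in a double-blind trial with matched capsules.
- **That the imputation is meant to repair the complete-case result in Table 48.** SAP 6.5 and 8.3.3 present the analyses with and without imputation as checks of robustness.
- **That missing at random fails for everyone imputed.** Subjects whose Day 11 improvement is missing are not affected by this omission.
- **That the main conclusions are touched.** The primary analysis does not use this model, and the Day 5 DOOR list uses the right visit.

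**What to change.** In SAP 8.4.2, state that the Day 11 list uses observed OCO at Day 11, observed clinical improvement at Day 11 and the Day 11 visit day centered at 11, with Day 5 OCO and clinical improvement kept as additional predictors. Give their positions, since the list is ordered. The existing rule that drops variables missing for a subject then covers those without Day 11 status. Keeping the Day 5 predictors alongside the Day 11 ones was not itself simulated. The cost is one sentence and a changed variable list; no new data are needed.

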9. SAFETY EVALUATION

Subjects in safety analyses will be analyzed according to randomization assignment, using the safety analysis population.

9.1. Demographic and Other Baseline Characteristics

Summaries of age, gender, ethnicity, race will be presented for the PCT \leq 0.25 ng/mL cohort by site (Table 13 and Table 15) and by treatment group and overall (Table 17 and Table 18). Similar tables will be presented for the PCT $>$ 0.25 ng/mL cohort by site in Table 14 and Table 16. Age will be summarized as a continuous variable. Ethnicity will be categorized as Hispanic or Latino, or not Hispanic and not Latino. In accordance with NIH reporting policy, subjects may self-designate the subject as belonging to more than one race or may refuse to identify a race, the latter reflected in the CRF as “No” to each racial option. For subjects that were previously enrolled in this study, only information associated with their second enrollment will be reported and used for analysis.

Individual subject listings will be presented for all demographics and baseline characteristics (Listing 6).

9.1.1. Prior and Concurrent Medical Conditions

Summaries of subject’s medical history will be presented by MedDRA[®] system organ class (SOC) and treatment group (Table 19).

Physical assessment findings from the enrollment visit, and any follow up visits, will be included in Listing 7.

9.1.2. Prior and Concomitant Medications

All concomitant medications taken within 30 days of signing the informed consent or during the study period will be recorded. Concomitant medications will be coded to the Anatomical Therapeutic Classification using the WHO Drug Dictionary. A by-subject listing of concomitant medication use will be presented (Listing 15). The use of concomitant medications during the study will be summarized by ATC1, ATC2 code and treatment group (Table 73).

9.2. Measurements of Treatment Compliance

Subjects were administered a PCT test to measure their PCT levels. Only subjects with PCT levels PCT \leq 0.25 ng/mL were randomized to receive azithromycin or placebo. The number of subjects will be tabulated by site, treatment group, and time period of PCT screening (Table 10). Subjects were to take a single dose of the study product within 24 hours of randomization and once daily for four days. Review of the memory aid, checking of the study product container, and interview with the subject will be utilized to check treatment compliance. The number of doses of study product administered will be presented by treatment group (Table 11 and Listing 8). A listing of all subjects who took at least one dose of study product is provided in Listing 1.

9.3. Adverse Events

When calculating the incidence of AEs over multiple days (i.e., on a per subject basis), each subject will only be counted once and any repetitions of AEs within a subject will be ignored; the denominator will be the total population size on the first day of the time period (Day 1). For tabulation of AEs by day, the denominator will be the number of subjects enrolled and not withdrawn from the study by the day being described. All AEs reported will be included in the summaries and analyses.

9.3.1. Solicited Events and Symptoms

Solicited events will be captured from Day 1 until Day 11. For those with multiple solicited events, the ordinal response table will be based upon the most severe solicited event.

Solicited events were recorded for trial Days 1-11, or until study completion or termination, as the maximum severity for each day. Target solicited events include abdominal pain, vomiting, diarrhea, allergic reaction, and candidiasis.

The proportion of subjects in each treatment group experiencing each solicited event will be tabulated by treatment group (Table 65). The proportion of subjects in each treatment group experiencing each solicited event will be tabulated by treatment group and severity (Table 66). The proportion of subjects in each treatment group experiencing each solicited event will also be tabulated by day and severity level (Table 67 and Table 69). Finally, solicited events will be analyzed by taking the most severe response over the follow-up period, dichotomizing into a binary variable (mild or greater, moderate or greater, severe) (Table 68). Proportions for these derived binary variables will be reported along with 95% CIs using the Wilson method. Comparisons of proportions by treatment groups will be given as risk differences (with 95% CIs from the Miettinen–Nurminen method) and p-values from Fisher’s Exact Test.

The maximum severity occurrence of each solicited event (proportion of subjects for each severity level) will be plotted for each solicited adverse event (Figure 27). Solicited events by subject will also be presented (Listing 9).

9.3.2. Unanticipated Adverse Device Effects

Any UADEs will be collected from the first study enrollment through study completion. When calculating the incidence of UADEs (i.e., on a per subject basis), each subject will only be counted once at the highest severity and/or relationship, and any repetitions of UADEs within a subject will be ignored; the denominator will be the total number of subjects in the safety population. All UADEs reported will be included in the summaries and analyses in Table 70.

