## **7.4 Follow-up for Non-randomized Subjects**

### **7.4.1 Visit #5N (Day 28+7)**

At enrollment, subjects with a PCT level > 0.25 ng/ml will still have data and samples collected but they will not be randomized. Their charts will be reviewed through 28 days after enrollment in order to support future use research. This may include recording the results of clinical laboratory evaluations as specified in Section 8.2.1. Review of medical history will be performed to determine whether medically attended visits or receipt of systemic antibiotics have occurred.

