#### **9.2.3 UADE Definition**

An unanticipated adverse device effect (UADE) per 21 CFR 812.3(s): is defined as any serious adverse effect on health or safety or any life-threatening problem or death caused by, or associated with a device if that effect, problem, or death was not previously identified in nature, severity, or degree of incidence in the investigational plan or application (including a

supplementary plan or application), or any other unanticipated serious problem associated with a device that relates to the rights, safety, or welfare of subjects.

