### **9.3.2 Reporting for Studies Conducted Under DMID Sponsorship**

Any UADEs will be collected from the first study enrollment through study completion. The Site Investigator is responsible for documenting and reporting all UADEs that are reported during the study, regardless of their relationship to study procedures.

Information to be collected includes a record of any concomitant medication, event description, time of onset, clinician's assessment of severity and relationship to study procedures/study device. All UADEs will be followed to adequate resolution or stabilization. Resolution of an UADE is defined as the return to pre-enrollment status or stabilization of the condition with the expectation that it will remain chronic. Time of resolution/stabilization of the event will be collected for device procedure related UADEs.

DMID will evaluate each report of a UADE in accordance with 21CFR812.46(b). DMID will notify the FDA, all participating site principal investigators (i.e., all principal investigators to whom the sponsor is providing study device), and all reviewing IRBs through the participating sites' principal investigators. Notification will occur as soon as possible but in no case later than 10 working days after the sponsor is notified of the UADE. Relevant follow up information to a safety report will be provided as soon as the information is available.

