6.3. Analysis Populations

The primary analysis will be done using the intention-to-treat (ITT) cohort. Other analyses may use according-to-protocol (ATP) cohorts. Analyses of the ITT cohort will include imputation for missing clinical improvement and DOOR.

Reasons for exclusion from each analysis population are summarized in [Table 9](#) and shown by subject in [Listing 5](#). Excluded subjects might satisfy multiple criteria justifying their exclusion but will have only one reason indicated in [Table 9](#) and [Listing 5](#). The exclusion reason indicated will be determined by first exclusion reason met based on the following rules in the order they are listed for each analysis population.

Safety Population Exclusions:

- Subject not treated with any dose of study product

ITT Population Exclusions:

- Non-randomized subjects

ATP Population Exclusions:

- Subject was excluded from ITT
- Subject had major protocol deviation related to I/E criteria
- Did not consume 5 doses of study product by D5V
- First dose of study product not taken within 24 hours of randomization
- Dosing not resumed within 24 h of a missed dose

ATP-5 Population Exclusions:

- Subject was excluded from ATP population
- Subject did not complete D5V
- D5V occurred out of the protocol defined window of Day 5 + 3 days
- D5V was not completed in person
- Data collected is insufficient to define clinical improvement at D5V

ATP-11 Population Exclusions:

- Subject was excluded from ATP population
- Subject did not complete D11V
- D11V occurred out of the protocol defined window of Day 11 + 3 days
- Data collected is insufficient to define clinical improvement at D11V

ATP-28 Population Exclusions:

- Subject was excluded from ATP population
- Subject did not complete D28V
- D28V occurred out of the protocol defined window of Day 28 ± 2 days
- Data collected is insufficient to define clinical improvement at D28V

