6.3.3. Safety Population

The Safety analysis population will consist of all subjects with recorded receipt of any amount of study product. The analyses on the Safety analysis population will be performed per treatment actually received.

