14.3.2 Listing of Deaths, Other Serious and Significant Adverse Events

Table 71: Listing of Unanticipated Adverse Device Effects - Safety Population

Adverse Event	Date of PCT Screening Test	No. of Days Post Associated PCT Test (Duration)	Reason Reported as an UADE	Severity	Relationship to Study Treatment	If Not Related, Alternative Etiology	Action Taken with Study Treatment	Subject Discontinued Due to AE	Outcome	MedDRA System Organ Class	MedDRA Preferred Term
Subject ID: , Treatment Group: , AE Number:											
Comments:											
Subject ID: , Treatment Group: , AE Number:											
Comments:											

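### Device effects (UADEs) are counted over, and listed for, subjects who took study drug, although every enrolled subject is exposed to the PCT test

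*SAP*

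**What the plan says.** **The device and who meets it.** The Protocol Summary classes the trial as an IDE study and names the VIDAS platform and PCT test as the diagnostic device. Protocol 9.2.3 defines a UADE as a serious effect "caused by, or associated with a device", so the device and not azithromycin is the exposure. Protocol section 5 has blood for PCT taken from all enrolled subjects. Those above 0.25 ng/mL "will still have data and samples collected but they will not be randomized" (Protocol 7.4.1).

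**Collection.** Protocol 9.3.2 states: "Any UADEs will be collected from the first study enrollment through study completion". It also asks for an assessment of relationship to the study procedures or device.

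**Analysis.** SAP 9.3.2 counts each subject once, says "the denominator will be the total number of subjects in the safety population", and then sends all reported UADEs to Table 70. SAP 6.3.3 defines that base: "The Safety analysis population will consist of all subjects with recorded receipt of any amount of study product". SAP 6.3 gives one reason for exclusion from it: "Subject not treated with any dose of study product". The Table 70 shell has columns for azithromycin, placebo and all subjects, with N taken from the Safety population. The listing shell is headed "Table 71: Listing of Unanticipated Adverse Device Effects - Safety Population".

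**Schedule.** Protocol Appendix A and SAP Table 4 mark UADE assessment at Visits 2 to 5 and at early termination. Neither marks it at Visit 5N, the chart review for non-randomised subjects.

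**The concern.** The numerator and the denominator are defined on different exposures. The numerator rule covers every reported device effect from first enrolment. The denominator covers drug takers. Three groups are tested with the device but never take study product:

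- subjects with PCT above 0.25 ng/mL, who stay enrolled without study drug;
- subjects who qualify but decline randomisation (Protocol section 4);
- subjects who are randomised but not dosed, whom SAP 6.3.1 foresees and keeps in the ITT population.

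A UADE in any of them has no proper place in the planned output. What is at stake is the device-safety statement of an IDE study: the reported incidence would not describe people exposed to the device, and the cohort that the test classifies as high would have no row or column.

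**Working it through.** **1. Can SAP 9.3.2 be carried out as written?** Take one UADE in a subject with PCT above 0.25 ng/mL.

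- If the rule to include all reported UADEs is followed, the event enters the numerator of Table 70. The subject is not in N, belongs to neither arm, and is not part of the all-subjects total, which is also Safety-based.
- If the Safety restriction is followed, the event leaves Table 70, and it leaves Table 71 by its title.

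The two instructions cannot both be met. A randomised but undosed subject has an arm, but the numerator conflict is the same.

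**2. Does another display cover it?** The SAP treats the high-PCT cohort explicitly elsewhere: Tables 6, 14 and 16, and a PCT-cohort column in Listings 3, 6, 7, 12 to 15 and 19 to 22. Tables 70 and 71 have no such column. Table 71 does give the PCT test date and the days since that test, so it is organised around the device, yet its causality column is relationship to study treatment. Protocol 9.3.2 asks for relationship to procedures or device.

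**3. How many tested subjects lie outside the base?**

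Inputs:
- 560 evaluable and 16.9% loss (Protocol 11.2);
- 674 randomised (Protocol 11.2);
- a ceiling of 840 enrolled (Protocol Summary);
- a 50% low-PCT share (SAP 4.3, given there for 420 randomised out of 840).

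The plan's own figure first: 560 / (1 − 0.169) = 673.9, so 674 is reproduced. It is an upper limit for the Safety N, because undosed subjects are removed from it. For the original design, 420 / 0.50 = 840 is also reproduced.

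| Scenario | Tested | Randomised | Not randomised | Share |
|---|---|---|---|---|
| Protocol ceiling | 840 | 674 | 840 − 674 = 166 | 166/840 = 19.8% |
| Original 50% share kept | 674/0.50 = 1,348 | 674 | 1,348 − 674 = 674 | 50% |

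The scenarios exclude each other: 1,348 exceeds the ceiling of 840, and 674/840 implies a low-PCT share of about 80%, not 50%, if nobody declines. Randomised but undosed subjects would add to the numbers outside the base; the documents do not say how many to expect.

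**4. Effect on a reported rate.** Suppose all UADEs among tested subjects are counted but divided by 674. The result exceeds the rate per tested subject by 840/674 = 1.25 in the first scenario and 1,348/674 = 2.0 in the second. One event is 1/674 = 0.148%, against 1/840 = 0.119% or 1/1,348 = 0.074%. With no events, the one-sided 95% upper bound 1 − 0.05^(1/N) is 0.44% for N = 674, 0.36% for N = 840 and 0.22% for N = 1,348.

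**The case against.** **Reporting does not depend on the tables.** Protocol 9.3.1 requires entry of any UADE within 24 hours of site awareness and a report to the IRB. Protocol 9.3.2 adds sponsor evaluation and notification of the FDA, the investigators and the IRBs. Neither section is limited to randomised subjects. The Visit 5N review already looks at medically attended visits, where a serious event would be likely to surface. This stands. A reader might infer that a UADE in the high-PCT cohort would go unreported; the documents do not support that. What is missing is a scheduled assessment and a valid place in the summaries.

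**Serious outcomes appear elsewhere.** A reader might also take UADEs to be the only serious events the trial reports. They are not. Deaths and hospitalisations are listed (Listings 18 and 20), the hospitalisation listing carries a PCT-cohort column and an intensive-care field, and the halting rules in Protocol 9.5.1 use admission and death. None of these displays gives UADE incidence.

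**A treated base has some logic.** The test is an in-vitro assay on a low-risk blood draw, and only in randomised subjects does its result lead to a blinded assignment. This could justify showing a treated subset. It cannot justify the only denominator, since the collection rule starts at enrolment and the inclusion rule covers all reports.

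**Size.** Two stronger figures are tempting: that at least 166 subjects are left out, and that half of device exposure is. The first fails because 840 is a ceiling, so with 674 randomised 166 is the most that can be non-randomised. The second applies the original design's 50% share to the revised target. The interim analysis was to check that share (Protocol 11.3.2, SAP 6.6), and no updated value is given.

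**Conclusion.** The mismatch is real and follows from the text alone. SAP 9.3.2 and Table 70 use a drug-exposed denominator for a device-defined event while including all reports, and Table 71 is confined to the same population and carries a drug-causality field. UADEs in non-randomised or undosed subjects would either fall outside their denominator or be dropped.

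The size is conditional. With 840 enrolled and 674 randomised it is 166 subjects (19.8%), plus any randomised but undosed. With fewer enrolled it is smaller. It reaches half only if the 50% share still holds and enrolment passes the stated ceiling. The 1.25 and 2.0 rate ratios assume that every UADE among tested subjects is captured and counted; the documents give no UADE rate. Protocol 9.3.1 calls such events unexpected, so few if any should occur. No hypothesis test uses UADE incidence, and the primary analysis is unaffected. The correction is still worth making, because it is cheap and the plan cannot be followed consistently without it.

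**What to change.** - **SAP 6.3 and 9.3.2:** add a device-exposed population, meaning all enrolled subjects with a PCT sample taken for the study, and make it the UADE denominator.
- **Tables 70 and 71:** use that population for N and for the listing title. Add a column (in Table 71, a group label) for subjects not randomised or not dosed, beside the two arms.
- **Table 71:** change the relationship field to study device or procedure, as Protocol 9.3.2 requires.
- **Protocol 7.4.1, Protocol Appendix A and SAP Table 4:** add a UADE item to the Visit 5N chart review.
- **Enrolled total:** state the number enrolled or expected alongside 674 randomised, so that the device-exposed N is known.

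The cost is some SAP wording, two table shells, and one item in a chart review that is already done. No further contact with subjects is needed.
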